The initial effects on pain, pain sensitivity, range of motion and muscle strength of an anteroposterior mobilization of the glenohumeral joint in overhead athletes with chronic shoulder pain

INTRODUCTION

Shoulder disorders are a common musculoskeletal condition, with an estimated lifetime prevalence of 42% in athletes performing highly repetitive overhead movements.³⁴ Shoulder symptoms are often persistent and recurrent, with 40-50% of patients reporting persistent symptoms after 6-12 months,⁵⁶ and 14% continuing care after 2 years.²⁸

Mobilization techniques are commonly used by physiotherapists for reducing pain and disability in patients with shoulder musculoskeletal disorders.^{5,9,17} One approach for mobilizing the shoulder joint is the Maitland's approach, where passive rhythmic oscillatory mobilizations are applied anywhere within the shoulder joint range of movement (ROM) and graded according to force, amplitude, direction and duration.³⁰ When applied specifically over the glenohumeral joint, the Maitland's approach includes both angular and translational mobilizations, with these latter being classified in terms of direction as anteroposterior (AP), posteroanterior and caudal mobilizations.²⁹

Humeral head AP mobilizations are often used with the intention to achieve mechanical effects on capsule extensibility, such as a stretching of posterior capsule tightness.^{16,27} Indeed, they can induce either a temporary or sustained elongation of the posterior capsule depending on the applied force³⁶ and an increase in shoulder ROM (i.e. shoulder external rotation).²⁰ Besides these mechanical effects, the application of an AP mobilization to the glenohumeral joint produced sympathoexcitatory effects (i.e.

increase in skin conductance, reduction in skin temperature) in healthy people⁴⁷ and in subjects with posterior capsule tightness.⁵⁹ However, the potential neurophysiological effects of this mobilization technique on other pain and function-related outcome measures have not yet been investigated. A greater understanding of the mechanisms underlying the beneficial effects reported after the application of shoulder AP mobilization techniques,^{10,20,31,40} would help clinicians for instance to identify those individuals more likely to respond to this manipulative intervention.¹

Previous studies have demonstrated positive effects in terms of improvement of shoulder ROM, pain sensitivity and muscle function (i.e. reduction on rotator cuff muscle activity) when applying an AP mobilization to the humeral head in the form of a mobilization with movement (MWM).^{43,51} Whether similar clinical effects might be obtained with an AP mobilization to the humeral head following Maitland's approach is unknown.

The aim of this study will be investigated the initial effects of a passive rhythmic AP mobilization applied to the glenohumeral joint on pain sensitivity and muscle function in overhead athletes with chronic shoulder pain. In addition, the effects of this technique on self-reported shoulder pain and disability and ROM will be also evaluated.

METHODS

A repeated-measures, double-blinded randomized, placebo-controlled study will be conducted to evaluate the initial effects of an AP mobilization of the glenohumeral joint on pressure pain threshold (PPT), muscle strength, self-reported shoulder pain and disability and ROM.

Participants

The overhead athletes aged between 18-60 years of age will participated in this study. Besides presenting with a history of chronic shoulder pain (i.e. lasting ≥ 3 months), athletes will required to play overhead sport regularly (at least once per week) in an organized way. Recruitment of potential volunteers will be conducted at the Student Sport Center *BLINDED* through poster advertisement. Volunteers who met the inclusion criteria will be then evaluated as they reached the laboratory.

Subjects will be excluded if they had a non-musculoskeletal origin of shoulder pain, previous surgery to the shoulder complex, frozen shoulder, any co-existing inflammatory, infectious or neurological condition that would exclude the patient from physiotherapy treatment, or any evidence of pain referred from the cervical spine to the shoulder.⁵⁵ In addition, they will be instructed to avoid any medication intake during the week prior to the study commencement and for the duration of the study.

Data collection took place at the *BLINDED* from february to march 2018. All participants will received an information leaflet and will gave written informed consent prior to the study beginning. The study was approved by the local Institutional Ethics Committee and all the procedures will be conducted according to the Declaration of Helsinki.

Outcome measures (dependent variables)

The outcome measures used in this study are: PPT, muscle strength, self-reported shoulder pain and disability, and shoulder ROM.

Pressure pain threshold (PPT)

A standardized protocol for evaluating PPT will be used.⁴⁴ One test site on the affected and non-affected shoulder (mid belly of the anterior deltoid, 5 cm caudal to the anterior border of the acromion) and one remote site on the ipsilateral tibialis anterior (5 cm inferior and 2.5 cm lateral to the tibial tubercle) will be selected for PPT measurement. All these points will be marked with a permanent marker and photographed so that the same points could be used for pre-and post-condition measures.

The PPT will be measured using an analogue Fisher algometer (Force Dial model FDK, Wagner Instruments) with a surface area at the round tip of 1cm². The algometer probe tip will be applied perpendicular to the skin at a rate of 1kg/cm²/s until the first onset of pain.¹² PPT will be measured three times on each site with a 30 s rest period between each repetition. The mean of the three measurements will be used in the statistical analysis.

Pressure algometry is a valid and reliable method to measure PPT with studies showing good repeatability of measurements on the shoulder.^{21,41}

Shoulder muscles strength

Isometric strength of the shoulder internal and external rotator musculature will be measured using a portable hand-held dynamometer (Nicholas Manual Muscle Tester, Lafayette Instruments, USA).

For external rotation testing, participants will be positioned in sitting with the shoulder in 0° of abduction and medially rotated 45° and the forearm in its mid-range of motion between supination and pronation.²⁴ The dynamometer will be placed on the lateral surface of the distal forearm just proximal to the ulnar styloid process and anchored by a belt to the handlebar of a glass suction cup on the wall. This ensured reliability when quantifying external rotation strength.²⁵ Subjects will be instructed to push in the direction of shoulder external rotation while maintaining the trunk in a stable position.

Shoulder internal rotation testing will be performed in standing using the Gerber lift-off position.¹³ The dynamometer will be placed on the distal aspect of the ventral forearm, between the patient forearm and the wall, which provided in this case the stabilization counterforce. Subjects will be instructed to lift the dorsum of the hand off the mid-lumbar region against the wall.

Participants will be instructed to exert as much force as possible against the dynamometer during six seconds (*make test*).⁴⁹ This process will be repeated three times with a 30-s rest period between measurements and the mean will be used in the statistical analysis.

Hand-held dynamometry by using fixed instrumentation is a reliable method for measuring strength of the internal and external rotator shoulder musculature.²⁵

Self-reported shoulder pain

Participants will be asked to indicate the intensity of their current shoulder pain using a numeric rating pain scale (NRPS). The NRPS has demonstrated good test-retest reliability and responsiveness to treatment in patients with shoulder pain.³³

Shoulder disability

The Spanish version of the Disabilities of the Arm, Shoulder and Hand (DASH) questionnaire will be used to record shoulder disability.¹⁵ The DASH is comprised of 30 items (disability/symptom section) and two optional sections related to the impact of pathology on work and sports.³² Each item is scored from 1 to 5 with increasing values representing more severity of symptoms. The total score for the disability/symptoms section ranges from 30 to 150, but it is then transformed to a scale from 0 (better score possible) to 100 (worse score possible).

The Spanish version of the DASH has shown high internal consistency, excellent test-retest reliability, good construct and criteria validity and excellent responsiveness to treatment.¹⁵

Shoulder range of movement (ROM)

Active elevation in the scapular plane and passive glenohumeral internal and external rotation will be measured using a Standard BASELINE[®] 12-inch plastic goniometer following previous guidelines.^{26,39}

For measuring active elevation in the scapular plane, participants will be in a standing position. A flat stiff board will be positioned 30° anterior to the frontal plane (scaption plane) to control the plane of elevation of the affected arm.⁴² Participants will be instructed to move the affected arm into full elevation while maintaining contact with

the stiff board. The goniometer will be positioned with the fulcrum placed at the midpoint of the central aspect of the glenohumeral joint, the stable arm parallel to the trunk, and the moving arm parallel to the longitudinal axis of the humerus.²⁶

For assessment of passive glenohumeral internal rotation, participants laid supine with 90° of shoulder abduction in the frontal plane and the elbow flexed at 90°. ¹¹ The examiner stabilized the scapula with one hand by applying mild pressure to its anterior aspect (coracoid process), while applying with the other hand a passive movement of shoulder internal rotation to its maximal point. An assistant read the measurement placing the goniometer with the stationary arm parallel to the floor and the mobile arm in alignment with the forearm starting at the olecranon.³⁹ The same starting posture and goniometer positioning will be used for measuring passive glenohumeral external rotation.

Experimental conditions (independent variables)

There are two independent variables in the research design: treatment condition and time (pre-, post-application). Treatment condition has three levels, which include the AP shoulder mobilization, a manual contact and a no-contact condition.⁴⁷ These experimental conditions will be administered in random order in three separated sessions to all participants, with each session separated by 48 h in order to control for carry-over effects.³⁵ The treatment allocation sequence will be randomized using sealed envelopes and concealed from the investigator who took the outcome measurements. An experienced physiotherapist with a Master degree on manual therapy and more than 10 years of working experience will apply all conditions. This physiotherapist will be blinded to the results of the measurements and questionnaires used as outcome measures.

All conditions will be applied for a total of 10 min, comprising three sets of 3 min, alternating with 30-s rests. Verbal instructions and positioning will be strictly standardized during all the sessions.

Treatment condition

The treatment condition consist on the application of a passive rhythmic AP mobilization to the glenohumeral joint of the affected shoulder. In particular, a Grade III AP glide to the humeral head with the arm positioned in 90° of glenohumeral abduction and full internal rotation was used.⁴⁷ The posterior gliding force to the humeral head was applied maintaining the glide at right angles to the plane of movement and at a frequency of 2 Hz which will be controlled by means of a metronome. The arm will be returned to its original position between each set.

Manual contact condition

During the manual contact condition the therapist positione the patient in a mid-range position of glenohumeral abduction and internal rotation and apply the hands to the same contact point as in the treatment condition. However, a simulated posterior glide will be performed but with minimal pressure actually applied.⁴⁷ The number of repetitions and sets were as per the treatment condition.

No-contact condition

During the no-contact condition, the subject remain in the initial starting position thorough the entire session but there are no manual contact between the therapist and the participant.⁴⁷ The total treatment time will be the same as per the other conditions.

Procedure

At the first session and after recording demographic data, the NRPS and DASH will be administered followed by PPT, ROM and muscle strength measurements in a standardized order. Subjects then will received the assigned intervention for that session and, immediately afterwards, all outcome measures will be reassessed following the same order as before. The only exception was the DASH, which will be assessed before and 24 hours after each experimental condition. This procedure will be repeated for all the three test sessions.

An investigator, will blinded to the allocated intervention, performed all the outcome measures before and immediately after the application of the three experimental conditions. Discussion between researchers and subjects will be minimized during treatment in order to facilitate subject blinding and reduce potential interactions. No feedback will be given on performance until after the final session. The extent of subject blinding will be assessed through a short, self-administered, post-experiment questionnaire, where participants will be asked to indicate whether they have experienced a physiotherapy treatment in any of the sessions and, if so, in which session.³⁵

Statistical analysis

Data will be analysed using SPSS 22 for Windows. Statistical significance will be set at $p < 0.05$.

Two independent variables will be incorporated into the research design: treatment (AP mobilization, manual contact, no-contact) and time (pre- and post-intervention). Five dependent variables will be considered including PPT, muscle strength, NRPS, DASH (disability/symptom section) and ROM.

Descriptive statistics will be calculated to describe baseline data. A two-way analysis of variance (ANOVA) through a General Linear Model and appropriate post-hoc tests of simple effects will be used to evaluate hypothesis that AP mobilization produced more changes than manual contact and no-contact conditions from pre- to post-intervention ($P=0.05$). The between subject factor will be treatment condition (AP mobilization, manual contact, no-contact) with time (pre and post-intervention) as within subject factors.

Sphericity will be confirmed by means of Mauchly's test. Bonferroni test will be used for multiple comparisons and the effect size will be estimated using Eta square (η^2) when significant. An effect size of 0.01 will be considered small, 0.06 medium and 0.14 large.⁷

REFERENCES

7. Cohen J. *Statistical Power Analysis for the Behavioral Sciences.* New York, NY: Routledge Academic, 1988.

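### The instruction to avoid all medication is wider than the outcomes need and, followed literally, tells an eligible athlete to omit unrelated prescribed treatment (minor participant-safety point)

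*Protocol*

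**What the plan says.** The medication rule is one sentence at the end of the eligibility paragraph in the protocol's Participants section. After the exclusions it says of the subjects that "they will be instructed to avoid any medication intake during the week prior to the study commencement and for the duration of the study". The protocol has no other medication rule.

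The same section defines who can fall under it:

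- On age: "The overhead athletes aged between 18-60 years of age will participated in this study".
- On source: "Recruitment of potential volunteers will be conducted at the Student Sport Center".
- On co-existing illness, the exclusion is "any co-existing inflammatory, infectious or neurological condition that would exclude the patient from physiotherapy treatment". The other exclusions concern the origin of the pain, earlier shoulder surgery, frozen shoulder and pain referred from the neck.

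It also describes the safeguards around participation: "All participants will received an information leaflet and will gave written informed consent prior to the study beginning", and "The study was approved by the local Institutional Ethics Committee and all the procedures will be conducted according to the Declaration of Helsinki".

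On design, the section on experimental conditions states: "These experimental conditions will be administered in random order in three separated sessions to all participants". The Statistical analysis section lists five dependent variables: pressure pain threshold (PPT), muscle strength, the numeric pain rating (NRPS), DASH and range of motion (ROM).

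**The concern.** A restriction on medicines makes sense in a study of pain threshold and pain ratings, because an analgesic taken before one session and not another could move the outcomes. That reason extends only to medicines that act on the outcomes. The sentence covers all medicines.

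What is at stake is the welfare of a participant who takes regular treatment for something unrelated to the shoulder. Blood-pressure or thyroid treatment would be examples; these are illustrations and do not come from the protocol. Such a person is told to go without that treatment from a week before the study until it ends, and the study gains nothing evident in return.

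**Working it through.** The protocol states no figure on this point, so the check sets its statements side by side.

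**1. Scope of the rule.** The instruction in Participants covers any medication. It is not limited by drug class, by purpose or by likely effect on an outcome, and no other section narrows it.

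**2. Scope that the outcomes require.** The five dependent variables are PPT, strength, NRPS, DASH and ROM. Analgesics, anti-inflammatories and muscle relaxants are the classes with an obvious route to these. Treatment for an unrelated condition, held at a stable dose, has no evident one. The rule is therefore wider than its purpose.

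**3. Whether an eligible person can be caught by the excess.** Entry runs from 18 to 60 years. A co-existing illness excludes only if it is inflammatory, infectious or neurological and would also rule out physiotherapy. A treated condition outside those three groups does not exclude, nor does one inside them that is compatible with physiotherapy. Regular medication is not on the list. An athlete taking unrelated prescribed treatment can thus meet every listed criterion and still receive the instruction.

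**4. What the sentence then tells that person.** Followed as written, it tells them to omit the treatment.

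**5. Whether the analysis would suffer if unrelated treatment continued.** Each participant receives all three conditions, with sessions "with each session separated by 48 h in order to control for carry-over effects". Treatment that is stable over that period is the same at each of a person's three sessions, so it does not favour one condition over another. The broad rule therefore brings no evident gain that would justify it.

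**6. Whether the rule as it stands harms the analysis.** It does not. It applies equally before and during all three conditions, and no estimate or error rate depends on it.

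**7. How many people are affected.** The protocol gives no count of participants on regular medication, so this cannot be calculated. Recruitment at a student sport centre, among people who play organised overhead sport at least weekly, suggests few.

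**The case against.** The case against raising this has several parts.

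- **Intent and safeguards.** The authors very probably had pain-relieving drugs in mind. Ethics approval, written consent, an information leaflet and adherence to the Declaration of Helsinki all make a literal application unlikely. The leaflet is not available here and may be narrower. This stands as a reason for modest confidence and a low rating. It does not alter the sentence, which is the only medication rule in the protocol.
- **Force of the wording.** The protocol instructs participants to avoid medication; it does not forbid it. That is correct. The point is put here as an instruction, and a reader should not infer an enforced ban.
- **Participation condition.** The sentence follows the exclusions and begins as an addition to them, so it can be read as a requirement that volunteers must be able to meet. On that reading a person on regular treatment simply does not take part. A reader might infer that turning such a person away is itself a fault. It is not a safety harm, and the requirement does stand in the eligibility paragraph. The concern rests only on the other reading, in which an enrolled athlete acts on the instruction.
- **Simplicity.** A blanket rule avoids drug-by-drug judgement in a short study. This has some force, and it is met by naming three classes in place of an open-ended category.
- **Timing.** The Participants section reports data collection in February to March 2018 in the past tense, although most procedures are written in the future tense. If the study is finished, no participant benefits from a change. This stands and limits the practical value of the point.

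**Conclusion.** The point holds as a minor one about the wording of a single sentence. The stated rule is broader than the outcomes require and, taken literally, asks an eligible athlete to omit unrelated prescribed treatment. This is a fault in what the protocol fixes, and not a detail left to another document.

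It is worth considering as an inexpensive improvement and no more. There is no consequence for bias, power or analysis. The number affected is unknown and probably small. The exact length of the medication-free period does not matter, since the wording is too broad at any length.

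A reader might infer that participants were in fact made to stop essential treatment. The protocol does not support that: it identifies no such participant, the leaflet is not shown, and the ethical safeguards point the other way. Nor does it support any inference that the results are compromised.

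The conclusion assumes that nothing in the unseen leaflet already limits the instruction. If the leaflet does, only the protocol sentence needs to be aligned with it.

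**What to change.** In the Participants section, replace the reference to any medication with *analgesics, anti-inflammatories and muscle relaxants*, and keep the stated period. Then add: *Stable prescribed treatment for other conditions is continued unchanged; people who cannot safely stop a restricted medicine are not enrolled.* Check that the participant leaflet says the same.

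The cost is one reworded sentence and, if needed, a matching line in the leaflet. There are two downsides. Some participants stay on stable unrelated medication, which is constant across their three sessions. A few people who cannot safely stop a restricted medicine are not enrolled. If data collection is already complete, the change applies only to reuse of the protocol.

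### The three-session crossover is analysed with treatment and time only; leaving out session costs precision if pre-to-post change differs by session, and the orders are not stated to be balanced.

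*Protocol*

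**What the plan says.** Under *Experimental conditions (independent variables)* the protocol describes a three-period crossover: "These experimental conditions will be administered in random order in three separated sessions to all participants". On how the order is drawn it says: "The treatment allocation sequence will be randomized using sealed envelopes and concealed from the investigator who took the outcome measurements". It mentions no blocks, Latin square or equal sequence counts, and it excludes none of these. The gap between sessions has one stated purpose: "with each session separated by 48 h in order to control for carry-over effects".

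The factors are listed in that section ("There are two independent variables in the research design: treatment condition and time (pre-, post-application") and again under *Statistical analysis* ("Two independent variables will be incorporated into the research design: treatment (AP mobilization, manual contact, no-contact) and time (pre- and post-intervention"). The same section names a two-way ANOVA and assigns the roles: "The between subject factor will be treatment condition (AP mobilization, manual contact, no-contact) with time (pre and post-intervention) as within subject factors". The hypothesis is that "AP mobilization produced more changes than manual contact and no-contact conditions from pre- to post-intervention".

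Under *Procedure*, session 1 goes from demographic data and the questionnaires straight to the recorded threshold, range-of-motion and strength measures. No practice trial is described. For the later sessions: "This procedure will be repeated for all the three test sessions".

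**The concern.** In a three-period crossover, session is a known source of variation that the design makes easy to remove. Here the list of factors is closed at two, so this is a stated analysis choice and not a detail left open.

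Some outcomes depend on effort or judgement: a maximal push against a dynamometer, the first onset of pain under pressure, and active elevation. Each is measured before and immediately after the condition. If participants gain more from practice within session 1 than within later sessions, that extra gain is part of the change recorded for whichever condition came first. Across participants it becomes unexplained variation in the contrast between conditions. In a particular allocation, one condition may also come first more often than another. The 48-hour gap is aimed at carry-over and does not deal with this.

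At stake is the precision of the comparison of mobilization with the two control conditions.

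**Working it through.** The plan has no figure to reproduce: it states no sample size, SD, effect or power. The inputs are therefore assumptions.

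**Inputs**
- Three conditions, three sessions, and change from pre to post as the quantity compared (protocol).
- Orders drawn independently and uniformly from the six possible (assumed; the protocol says only that order is random).
- s: within-person SD of a session's change, independent between sessions (assumed).
- L: extra pre-to-post change that occurs only in session 1, taken as 0, 0.25, 0.5 and 1.0 s (assumed).
- n = 18 and n = 30 (assumed).
- A within-subject analysis of change (assumed; the protocol's text declares treatment between-subject).

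**Step 1. What cancels.** If a session shifts pre and post by the same amount c, then (post + c) − (pre + c) = post − pre. Only a session effect on the change itself matters.

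**Step 2. Variance of a pairwise contrast.** For one participant, session 1 adds +L, −L or 0 to the difference between two conditions, each with probability 1/3. Its mean is 0 and its variance is 2L²/3. The remaining variance of the difference is 2s². Hence:

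variance ratio = (2s² + 2L²/3) / 2s² = 1 + L²/(3s²)

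| L | variance ratio | rise in SE |
|---|---|---|
| 0 | 1.000 | 0% |
| 0.25 s | 1.021 | 1.0% |
| 0.5 s | 1.083 | 4.1% |
| 1.0 s | 1.333 | 15.5% |

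These ratios do not depend on n.

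**Step 3. Uneven order in one allocation.** The chance error in a contrast has mean 0 and SD L·√(2/(3n)). That is 0.19 L at n = 18 and 0.15 L at n = 30. Two given conditions differ by at least 20% of n in how often they come first with probability 0.31 (n = 18) or 0.22 (n = 30).

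**Step 4. Simulated power.** Each setting used 2,500 trials, a true difference of 0.75 s and two-sided 5% tests. Monte Carlo SE is at most √(0.25/2500) = 0.01.

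| n | L | random order, no session term | balanced, no session term | random order, session term | balanced, session term |
|---|---|---|---|---|---|
| 18 | 0 | 0.597 | 0.588 | 0.577 | 0.586 |
| 18 | 0.5 s | 0.540 | 0.558 | 0.549 | 0.594 |
| 18 | 1.0 s | 0.458 | 0.458 | 0.548 | 0.582 |
| 30 | 0 | 0.805 | 0.816 | 0.786 | 0.813 |
| 30 | 0.5 s | 0.780 | 0.800 | 0.794 | 0.824 |
| 30 | 1.0 s | 0.686 | 0.703 | 0.798 | 0.807 |

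With random order and no session term, the mean estimate was 0.74 to 0.76 for a true 0.75, and type I error was 0.045 to 0.053. With balanced orders and no session term, type I error fell to 0.025 at L = 1.0 s. Balance removes the session effect from the estimate but leaves it in the residual, so the test is conservative.

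**The case against.** Several points on the other side stand.

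- **Balance.** A reader might infer that the order is unbalanced. The protocol does not say so: sealed envelopes can hold equal numbers of the six orders, and how the list is built is often documented elsewhere. Only *not stated to be balanced* is supported.
- **Bias.** A reader might infer a biased comparison or an inflated error rate. Because order is randomised, the expected error is zero, and type I error stayed near 0.05. Nor is there a bias on top of a precision loss. At L = 0.5 s the chance error has an SD of 0.289 times the contrast's no-session-effect standard error, and 0.289² = 0.083 is the same 8.3% variance inflation.
- **Scope.** A reader might infer that every contrast suffers. A shift equal at pre and post cancels. There is little reason to expect learning in the pain rating, the DASH or the two passive rotation measures.
- **Size.** The protocol does not say that learning occurs. Strength and threshold values are means of three repetitions with rests, instructions are standardised, and no performance feedback is given until after the last session. These features weaken the case for a large session-1 gain but do not exclude one.
- **Priority.** Declaring treatment a between-subject factor, when everyone receives all three conditions, is a separate and more serious error.

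These points limit the harm. They do not supply a reason to leave session out of the model.

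**Conclusion.** The point holds as a matter of precision. The protocol fixes a model without session for a three-session crossover, and any difference between sessions in pre-to-post change then goes into the error term. The loss is nil if there is no such difference, small up to 0.5 s (4.1% in the standard error), and material near 1.0 s (15.5%). At 1.0 s, both repairs together raise power from about 0.69 to 0.81 at n = 30 and from about 0.46 to 0.58 at n = 18. At 0.5 s the gain is about 4 to 5 points, and at 0 there is none.

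These figures rest on assumed values of n, L and the true difference, and on a within-subject analysis. The session term is the main repair. Correcting treatment to a within-subject factor would not by itself bring session into the model.

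**What to change.** 1. *Statistical analysis*: in the within-subject comparison of pre-to-post change between conditions, add session (1, 2, 3) as a factor. This presupposes that treatment is first restated as within-subject.
2. *Experimental conditions*: state that participants are allocated to the six possible orders in permuted blocks of six, using the same sealed envelopes. Orders will then be as near equal as the final n allows; they will be exactly equal only if n is a multiple of six and nobody drops out.

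The two changes belong together, because balance alone leaves the test conservative. The cost is two residual degrees of freedom (2n − 2 becomes 2n − 4, so 58 becomes 56 at n = 30) and a different allocation list. If there is no session effect, the simulations show at most about two points of power lost with unrestricted random order, and no clear loss with balanced orders. No extra participants or visits are needed. A practice repetition before the first recorded measures would be an optional extra; the point does not depend on it.
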